## 2. Introduction

### 2.1. Background and Rationale

Recovery following general anesthesia is a complex issue confounded by the type of surgery, inflammation, different anesthetic drugs and techniques, patient co-morbidities, and differing patient and clinician perceptions of what constitutes good recovery.

Recovery is not a single entity but rather covers many aspects or domains such as physiological recovery, pain and nausea, emotion and mood, return to normal life or work activities, and cognitive function. It is an entity that is difficult to quantify, which then makes it difficult to study in a systematic manner. For anesthesiologists, poor recovery is often relayed by the surgeon days or weeks after the event, and it is usually categorized as an adverse outcome.

Research tools such as the Aldrete (1) or the QoR (2, 3) scales, focus on early physiological recovery, or the immediate perioperative period. These recovery scores are not sensitive enough to measure the rate of recovery (change over time) and have not been designed for repeated measures. They are also inadequate to identify poor cognitive recovery.

In 2007, an international group of anesthesiologists and neuropsychologists formed an advisory board to create a new quality of recovery scale. The aim was to produce a tool that was simple to perform, but sensitive enough to detect change in multiple domains of recovery over time. The initial validation experiment included over 700 patients, and this work has been published in *Anesthesiology*. It is called the Postoperative Quality Recovery Scale (PostopQRS) (4). Six domains of recovery are identified: physiological, nociceptive (pain and nausea) emotive (anxiety and depression), functional recovery (return of activities of daily living), cognitive recovery, and an overall patient perspective domain including satisfaction. The scale is completed prior to surgery to provide baseline values, and then repeated at

user-defined intervals. From some of the subsequent discriminant validation studies, time points have included early and late measures such as 15 minutes, 40 minutes, 1 and 3 days, and 3 months after the completion of anesthesia (typically defined as after the last surgical stimulation). Recovery is broadly defined as return to baseline values or better, except for the cognitive domain where a tolerance factor is included to allow for normal performance variability, such that patients are allowed to perform a little worse than baseline as still be scored as recovered (5). Because repeated tests tend to have a learning effect, the cognitive domain uses parallel forms, and only a small learning has been shown (5).

One of the most important benefits of the PostopQRS scale is that it enables recovery to be quantified and measured. This makes it possible to compare different interventions with the express purpose of developing clinical interventions to improve quality of recovery. The PostopQRS offers a tool to provide the recovery process to be examined. There are no other tools in existence that provide a comprehensive, sensitive assessment of the multiple aspects or domains of recovery, and is yet relatively simple to perform. Validation studies have been performed and show good discriminative ability (5-8). Ease of use is facilitated by using a web-based data entry system and the ability to use the telephone to conduct surveys after discharge from hospital. Telephone survey has been shown to be equivalent to face to face interviews using the PostopQRS (5). Further, the PostopQRS allows users to drill down to identify which recovery domain is affected for individuals in real time as well as for group audit.

### **Quality of recovery after operative laparoscopy**

The majority of the literature compares different operative techniques with outcome measures aimed at specific complications or length of stay. Few studies include quality of recovery or quality of life measures as secondary endpoints (9-12). However, for potential benefits relating to the use of sugammadex, there are a few studies primarily centered around deep neuromuscular block (DNB) facilitating low intraabdominal inflation pressures. Most outcomes relate to operative conditions with little data on patient

centered outcomes especially after discharge. The inclusion of sugammadex is to permit the use of DNB, and most comparative groups (of moderate block) are reversed with neostigmine.

It has been shown that more patients can be operated on with low intraabdominal pressure with DNB, and that operative conditions are rated as better in more patients with DNB (13, 14), though it is not absolute and there are frequent crossovers. That is, there are patients with moderate block and low pressure, and equally patients with DNB requiring high inflation pressures. The very few data on patient centered outcomes show reduced pain and nausea after DNB (13, 15-17), but lack of evidence of benefit for other recovery outcomes. This paucity of data has been stressed by review articles and editorials that DNB is associated with a modest effect on improving operating conditions but very little data to identify recovery benefits (13, 18)

### **Sugammadex is an effective drug to reduce deep neuromuscular blockade**

There is no clinical question that sugammadex is highly effective in reversing neuromuscular blockade with rocuronium or vecuronium. This has been the subject of a Cochrane review which included 18 randomized trials, showing that sugammadex can reverse blockade with rocuronium or vecuronium independent on the depth of block, and superiority to neostigmine (19). This aspect of sugammadex does not require further study. This translates to a low incidence of residual blockade in the PACU compared to neostigmine reversal. The "safety" benefit to using sugammadex has been proven, but this does not necessarily translate into better outcomes. Sugammadex, however, is an enabling drug to facilitate deep neuromuscular blockade, allowing the anesthesiologist to continue that block until the end of surgery and reliably reverse the block. This is just not possible with neostigmine reversal, as one must wait until a train of four count of at least 2 twitches (or TOF ratio > 0.7) to safely reverse the block with neostigmine.

## 2.2. Objectives and hypothesis

### **Objectives**

1. To identify whether the rate/quality of recovery is affected by deep neuromuscular block (DNB) and reversal with sugammadex versus light/moderate neuromuscular block reversed with neostigmine in patients undergoing operative gynecological or abdominal laparoscopic surgery of at least 1-hour duration.

### **Hypothesis**

1. The technique of deep neuromuscular block and reversal with sugammadex will result in improved quality of recovery, including cognition, compared to the current standard of care technique using light/moderate neuromuscular block reversed with neostigmine in patients undergoing operative gynecological or abdominal laparoscopic surgery of at least 1-hour duration.

### 3. Study Methods

#### 3.1. Trial Design

Parallel randomized trial with allocation ratio 1:1. The trial was registered prior to commencement and conforms to CONSORT guidelines.

The study was conducted in secondary and tertiary hospitals, which included an active laparoscopic surgery unit for gynecology and abdominal surgery.

#### 3.2. Randomization

The randomization sequence was produced using a computer-generated randomization sequence, in unequal blocks and stratified for gynecological and abdominal surgery. Concealment was undertaken by placing the card containing the allocation information in double opaque sealed envelopes, and concealment was maintained until after recruitment and the patients was admitted to the operating theatre. The treating anesthesiologist opened the envelopes to reveal the allocation. A non-participant in any process of the study prepared the envelopes prior to recruitment. A copy of the randomization sequence was stored in a separate databank, which is password protected and not made available to the investigators until the completion of the study.

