This introduces the concept of bundling agents together which have similar offset properties, and comparing that to real-world practice of light/moderate block, reversal with neostigmine and typically using sevoflurane as the maintenance anesthetic. The group receiving short acting drugs should have much less variance between effective block reversal and emergence, whilst at the same time facilitate optimal operating conditions. The coupling of agents should provide the greatest group separation for the use of sugammadex and potentially for postoperative quality outcomes.

In this study, we wish to primarily investigate the effect of the role of DNB, and to reduce the potential for confounding from different anesthetic techniques, we will standardize the anesthetic to use the shortest acting anesthetic bundle, and use desflurane coupled with short acting opiates and multimodal analgesia in patients undergoing operative gynecological or abdominal laparoscopic surgery of at least 1-hour duration.

The research team

The team will be managed by [name] at the University of Melbourne. [name] is one of the founders of the PostopQRS and is the co-director of the group. We aim to recruit centers with high volume of operative gynecological or abdominal laparoscopic surgery. The University of Melbourne department is co-located with the Royal Melbourne Hospital and the Royal Women's Hospital, and connected to our specialist cancer hospital the Peter MacCallum Cancer Center. We also have access to a private hospital (Northpark Private Hospital) which has a high volume of gynecological surgery. These centers will be the initial target hospitals with potential to expand the number of hospitals once the trial is underway. The team statistician is

[name], Statistical Consulting Centre, Department of Mathematics, The University of Melbourne.

Clinical significance

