
2.5 Study Procedures
	
Interventions
 
Common management will include the following
 
 1. Pre-medication other than oral analgesic (such as paracetamol) will not be used. 2. Induction will be with intravenous propofol, including co-induction consisting of fentanyl 0.5-3.0 mcg/kg, or equivalent short acting opiate including remifentanyl. 3. Analgesia will consist of multimodal analgesia as determined by the anesthesiologist to treat the degree of pain, but in principle to avoid long acting opiates, e.g. use intraoperative short acting opiates, 1 g acetaminophen qid, NSAID's including Cox II inhibitors (such as paracoxib 40mg i.v.), or oxycontin 10-20mg 6 hourly. 4. Dual antiemetic therapy as per hospital guidelines 5. The maintenance anesthetic will be desflurane, and will be titrated to effect by the attending anesthesiologist 6. Rocuronium administration: for moderate neuromuscular block an initial dose of 0.6 mg/kg, with repeat doses of 0.15mg/kg given if the TOF >2 twitches. After completion of the majority of surgical resection, the level of block may be reduced to at least 3 twitches in preparation for the end of surgery. 
For DNB, the initial dose will be 1.2 mg/kg and repeat doses of 0.15 mg/kg until PTC ≤ 2. TOF counts may be checked as frequently as every 15 seconds, but the PTC count interval must be at least 2 minutes (26).
 
 7. If vecuronium (a similar steroidal muscle relaxant) is used instead of Rocuronium, then the dose is reduced to 10% of the dose of rocuronium, and titrated to achieve the same TOF endpoints. 8. Reversal of neuromuscular block 
 a. Neostigmine 50 micrograms/kg coupled with atropine 20 micrograms/kg or glycopyrrolate 5 micrograms/kg, to a maximum dose of neostigmine of 5.0 mg. The neostigmine should not be administered until the TOF has at least 3 twitches present. b. Sugammadex dosage will be adjusted to body weight and PTC/TOF count at the time of reversal, and not administered until PTC at least 1. Dosage will be 4mg/kg if TOF = 0 and PTC ≥ 1; and 2 mg/kg if TOF ≥1. 9. Extubation for all groups will occur when the TOF has 4 twitches with no visible fade, (or a TOF ratio > 0.7 for institutions using a TOF ratio measurement device) adequate respiration and degree of alertness as determined by the anesthesiologist 																

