
2.6 Study Duration
	
Anticipated time-line
 
The aim is to recruit an average of 4-6 patients per week (at least 4 hospitals to participate, with potential to add more hospitals). That timeline for the study schedule is listed below, though could advance earlier if recruitment is faster than anticipated.
 
  
 Objective	3 months	3-12 months	12 -21 months	21-24 months	
   
 Ethics	XXXXXXXX				
 
 Recruit 40%		XXXXXXXXXX			
 
 Recruit 100%			XXXXXXXXXX		
 
 Complete 3 month follow up				XXXX	
 
 Analysis and manuscript					
  
	Objective	3 months	3-12 months	12 -21 months	21-24 months	Ethics	XXXXXXXX				Recruit 40%		XXXXXXXXXX			Recruit 100%			XXXXXXXXXX		Complete 3 month follow up				XXXX	Analysis and manuscript				
Objective	3 months	3-12 months	12 -21 months	21-24 months																											
Ethics	XXXXXXXX																														
Recruit 40%		XXXXXXXXXX																													
Recruit 100%			XXXXXXXXXX																												
Complete 3 month follow up				XXXX																											
Analysis and manuscript																															

2.7 Statistical Analysis and Sample Size Justification
	
The team statistician is [name], Statistical Consulting Centre, Department of Mathematics, The University of Melbourne, who will oversee the statistical analysis.
 
Study size
 
Sample size estimates are based on the primary outcome of cognitive recovery at 1 week after surgery, and a clinically important difference in cognitive recovery at 1 week
																														

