### 3.4. Framework

Two-center double-blind, placebo-controlled, parallel-group, randomized, phase IV study with 1:1 allocation ratio.

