## 6.2. Analysis Methods

A Fisher's Exact test was used to analyze the primary outcome of cognitive recovery at week 1 following laparoscopic surgery. A Generalized Linear Mixed Model (GLMM) test was used to analyze the recovery within and across all domains over time, including patient satisfaction. For the secondary outcomes, GLMM was used for analysis of the recovery domains and a T test was used for continuous data.

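### The primary analysis uses neither the stratification factor (surgery type) nor hospital: the test stays valid, but some precision is given up for no benefit

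*SAP*

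**What the plan says.** **Randomisation.** Protocol 2.7 and SAP 3.2 give the same rule: the sequence is generated "in unequal blocks and stratified for gynecological and abdominal surgery". Surgery type is the only stratification factor. Allocation cards are in sealed envelopes opened in theatre. Neither document says whether each hospital held its own set.

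**Hospitals.** Protocol 2.6 plans for "at least 4 hospitals to participate, with potential to add more hospitals". SAP 3.4 describes a "Two-center double-blind, placebo-controlled, parallel-group, randomized, phase IV study", and SAP 3.1 states that "The study was conducted in secondary and tertiary hospitals". The number differs, but both documents describe a multi-centre trial.

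**Analysis.** SAP 6.2 states: "A Fisher's Exact test was used to analyze the primary outcome of cognitive recovery at week 1 following laparoscopic surgery". Protocol 2.7 names the chi-squared test instead. Neither is set up with strata. SAP 6.2 assigns a GLMM to the recovery domains without listing its fixed or random terms, and a t test to continuous data. SAP 6.4 says that there is no further analysis.

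**The concern.** A factor used to restrict randomisation should normally appear in the analysis. Stratification makes the arms more alike than simple randomisation would. A test that ignores this uses a standard error that is too large whenever the strata differ in outcome.

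Hospital is a second natural factor. If recovery differs between hospitals and nothing ties allocation to hospital, the arms will differ by chance in their hospital mix, and an unadjusted test treats the resulting variation as noise. At stake is the width of the interval for the treatment difference and a small amount of power. Both can be recovered from data the trial already holds.

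**Working it through.** **Inputs.** From SAP 3.3: 85% recovery in the better arm, a 15-point difference (so 70% in the other arm), two-sided alpha 0.05, power 90%, 161 per group, 350 in total. Assumed, because the documents give no value: two equal groups (hospitals or surgery types) whose recovery rates differ by d in both arms.

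**1. The plan's own figure.** The average rate is 0.775.

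n = [1.96 × √(2 × 0.775 × 0.225) + 1.2816 × √(0.85 × 0.15 + 0.70 × 0.30)]² / 0.15² = (1.1575 + 0.7445)² / 0.0225 = 160.8, so 161 per group. This reproduces. Power at 161 is 90.04%. The step from 322 to 350 allows for 1 − 322/350 = 8.0% non-completion.

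**2. Size of chance hospital imbalance.** With two equal hospitals and allocation not tied to hospital, the between-arm difference in hospital share has SD √(0.25 × 2/161) = 5.6 points. At d = 20 points this moves the treatment difference by an SD of 0.20 × 5.6 = 1.1 points. The planned standard error is √(0.3375/161) = 4.6 points, where 0.3375 = 0.1275 + 0.21. The 1.1 points are already inside the 4.6, because the binomial variance behind the sample size is the total variance. They are not added to it.

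**3. What adjustment for hospital gains.** Within groups, each arm's variance falls by d²/4, so the sum over arms falls from 0.3375 by d²/2. Adjusted power is Φ[(0.15 − 1.96 × s₀)/s₁], with s₀ = √[2(0.174375 − d²/4)/161] and s₁ = √[(0.3375 − d²/2)/161].

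| Assumed d | Variance removed | Patients of 322 | Power, unadjusted | Power, adjusted |
|---|---|---|---|---|
| 0 | 0% | 0 | 90.0% | 90.0% |
| 5 points | 0.00125/0.3375 = 0.4% | 1 | 90.0% | 90.1% |
| 10 points | 0.005/0.3375 = 1.5% | 5 | 90.0% | 90.5% |
| 20 points | 0.02/0.3375 = 5.9% | 19 | 90.0% | 91.7% |

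Simulation with 200,000 trials per setting agrees, with gains of 0.1, 0.4 and 1.7 points at d = 5, 10 and 20. Unadjusted chi-squared power stayed between 90.2% and 90.4% for d from 0 to 30 points. Across the simulations its type I error was 4.8% to 5.1%. Differences above 20 points are not used as a guide: at 30 points one group in the better arm would have 100% recovery.

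**4. The stratified factor, surgery type.** Here balance is already built in, so the estimate already has the smaller variance, but the unadjusted test still uses the larger one. Under no treatment effect the ratio of true to assumed variance is r = 1 − (d²/4)/0.174375, and type I error is 2[1 − Φ(1.96/√r)].
- d = 10: r = 0.986, type I error 4.8%.
- d = 20: r = 0.943, type I error 4.4% by this approximation, about 4.2% by simulation.

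At d = 20, unadjusted power is Φ[(0.15 − 1.96 × 0.0465)/0.0444] = 90.7%, against 91.7% adjusted. The power gain is thus about 1 point for surgery type, smaller than for a factor left free.

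**5. Fisher's exact test.** At 161 per group it has about 88% simulated power and type I error of 3.6% to 3.9%. That shortfall comes from the choice of test, not from omitting the factors, and is as large as or larger than the effects above.

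**The case against.** The strongest reply is that nothing is broken. The sample size uses the total binomial variance, so between-hospital variation is already paid for; the planned power is met and type I error is not inflated. This is correct. A reader might infer that chance imbalance between hospitals biases the result or costs planned power. The working shows neither.

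The evidence that hospitals differ is also thin. A reader might take the extubation and room-exit wording in Protocol 2.5, "for institutions using a TOF ratio measurement device", as proof of it. That wording is conditional. It does not say that the participating hospitals used different monitors, and it bears on residual block rather than on cognition one week later. Protocol 2.2 describes a private hospital "which has a high volume of gynecological surgery" and a link to a cancer hospital, but these are possible sites; the SAP does not name its two. Stratification already balances gynecological against abdominal surgery overall.

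Three further limits stand. If each hospital held its own envelopes, allocation was in effect blocked by hospital, so it cannot be said that nothing balances the arms there. For the GLMM, the absence of hospital is inferred from silence. And the SAP is written in the past tense, with SAP 3.6 placing the analysis after allocation was revealed, so replacing the primary test may now be a post hoc change.

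None of this answers the point on surgery type: the trial stratified on it and does not analyse by it.

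**Conclusion.** The point holds as a small, nearly free improvement. The primary analysis leaves out a factor the trial randomised by, and also hospital. The result is a slightly conservative test and some forgone precision, not bias, inflated type I error or a shortfall against the 90% target.

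The size rests on assumed differences between two equal groups. Up to 20 points, at most about 6% of the variance and 1.7 points of power are available from adjusting for a factor left free. With no difference, nothing is lost by adjusting. If surgery type and hospital overlap, as they would where one hospital does mainly gynecology, their gains overlap too and should not be added. The case is firmest for surgery type. For hospital it depends on differences the documents do not quantify and on an envelope arrangement they do not describe.

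**What to change.** - In SAP 6.2, analyse the primary outcome with a Cochran-Mantel-Haenszel test stratified by surgery type and hospital. Report the common risk difference with its 95% CI, which SAP 4.3 calls for and a Fisher p-value alone does not supply.
- List the GLMM terms and include surgery type and hospital as fixed effects in each model.
- Keep the unstratified test as a sensitivity analysis.
- State how envelopes were distributed between hospitals, and reconcile the number of hospitals between Protocol 2.6 and SAP 3.4.
- If allocation has already been revealed, keep the pre-specified test as primary and label the stratified result post hoc. Because the protocol and SAP name different unadjusted tests, say which one is the pre-specified test.

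The cost is SAP wording and one further analysis; no new data are needed, since surgery type and hospital are known for every patient. The one small downside is sparse strata if a hospital contributes few patients of one surgery type.

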#### 3.3. Sample Size

Sample size estimates were based on the primary outcome of cognitive recovery at 1 week after surgery, and a clinically important difference in cognitive recovery at 1 week after surgery of 15%. Estimates of cognitive recovery were based on prior PostopQRS research and using multiple ages and surgical cohorts. It was estimated that the cognitive recovery for this cohort and duration of surgery would be 85% if there was good recovery. Using a two-tailed estimate and Chi-squared analysis, alpha of 0.05, and power of 90%, with 1:1 allocation ratio; the sample size required to detect an absolute difference of 15%

was 161 per group, which was rounded up to a total sample size of 350 patients to account for potential non-completion of the study

### 3.4. Framework

Two-center double-blind, placebo-controlled, parallel-group, randomized, phase IV study with 1:1 allocation ratio.

### 3.5. Statistical interim analyses and stopping guidance

Due to the small study size, there was no planned interim analyses, nor stopping rules defined.

